Hypothesis 1b: Participants who remit with IPT or combination treatment will have fewer relapses over follow-up than those who remit with fluoxetine.

Aim 2:

Investigate key presumed mediators of the relationship between treatment and remission

Hypothesis 2a: For initial treatment with IPT, change in social support will mediate the relationship between treatment and remission—improved social support will be associated with remission

Hypothesis 2b: For initial treatment with fluoxetine, change in emotional reactivity will mediate the relationship between treatment and remission—decreased emotional reactivity will be associated with remission.

Aim 3: Identify demographic and clinical moderators of the relationship between treatment and remission.

Hypothesis 3a: Time or cost for transport between participants' residences and KCH, and other Kisumu County Ministry of Health facilities will moderate the relationship between treatment and remission—higher time/cost will decrease the effect of initial treatment with IPT relative to fluoxetine (more treatment visits required for IPT versus fluoxetine treatment).

Hypothesis 3b: Severity of MDD and/or PTSD symptoms among non-remitters will moderate the relationship between subsequent treatment and remission, such that higher severity will decrease the effect of treatment on remission for treatment switch relative to treatment combination.

Hypothesis 3c: Q learning will produce personalized treatment algorithms using the above or other moderators.

Aim 4. Estimate the costs and cost-benefit ratios for fluoxetine and IPT treatment of depression and PTSD.

Hypothesis 4a: Pooled cost-benefit ratios will show that depression and/or PTSD treatment leads to net economic gain for individuals and households at month 6;

Hypothesis 4b: Separate analyses will find that IPT has a more favorable cost-benefit than fluoxetine at month 30.

Aim 5. Determine the acceptability and feasibility of delivering SMART-DAPPER treatments by telephone.

Hypothesis 5a. Telephone IPT will be acceptable and feasible.

Hypothesis 5b. Telephone fluoxetine provider appointments will be acceptable and feasible.

Aim 6. Determine the effect of telephone treatment delivery on retention in care.

Hypothesis 6a. Participants who elect to receive telephone treatment will have higher retention in care than those who receive face-to-face care.

Significance

The results of the proposed research will be significant in two ways:

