that which we are using to assess informal and formal income in our current effectiveness-implementation study in Kisumu, and that our research team is using across East Africa to assess the economic impacts of other health interventions. Employment gains in the informal and agricultural sectors will be converted to monetary values using imputed wages in the local labor market. Based on prior research that shows a strong linkage between mental health and economic outcomes,(Lund et al., 2011) we believe that assessing the economic benefits of depression treatment is essential for conducting a comprehensive cost-benefit analysis. To the extent that treatment results in changes in mortality (all-cause, whether or not suspected as suicide), we will incorporate these effects using the “full income” approach(Jamison et al., 2013), which attaches a financial value to each year of life lost.

Estimation of non-intervention control. For ethical reasons, our study does not include a non-treatment control. However, for complete cost-benefit analysis, we will compare the interventions to current (mainly absent) depression management. We cannot compare patients to their own baseline condition, since the natural history of untreated depression involves (at least episodic) clinical resolution in a substantial subset of individuals.(Whiteford et al., 2013) Instead, we will apply findings on the association of evolving clinical status and economic status in the intervention arms to historical data on the natural history of depression in these settings. In other words, we will make the conservative assumption that the changes in productivity associated with clinical resolution of the depression episode following treatment can be applied to untreated patients who eventually remit.

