consistent with the original R01 submission and responsive to reviewers' comments (summary statement response) on our funded U01 (DAPPER) study. While effectiveness data on treatment of depression in HICs (STAR*D) indicate that only approximately one-third remit with first line treatment, preliminary data from our current IPT study in Kisumu indicate remission rates over two-thirds. We will use a conservative estimate of the numbers entering the second randomization phase (non-remitters) and assume that half of study participants will need second-line treatment. Based on that estimate, the 968 participants randomized to the second stage of the SMART should represent 50% of those enrolled at the start of the trial, or 1936. Allowing for a 40% drop out rate across the 33 month duration of the study (domestic migration is common in Kenya³⁰), we will need 2710 participants for the SMART.

The additional number required for integration of the SMART design is 710 participants. Making a conservative assumption of ~20% prevalence of MDD and/or PTSD among primary care patients, we will screen 3,550 individuals to enroll 710 participants. While KCH and other Kisumu County Ministry of Health facilities see over 10,000 adult primary care patients per month, we will assume that only 20% of clinic attendees will undergo screening, and we will budget 3 months for recruitment. In order to avoid overwhelming mental health care providers, these 3 months of recruitment will be dispersed across a 18 month period: enrollment will halt when providers' caseloads are full and resume when at least 20% availability is regained. We will also work with Community Health Workers (CHWs) and Community Health Volunteers (CHVs) to

mobilize and sensitize the community about mental health services and refer community members to one of the health facilities for screening for the SMART-DAPPER study.

Eligibility criteria

Inclusion criteria:

- (1) KCH and other Kisumu County Ministry of Health facilities adult primary care outpatient clinic attendees who meet the threshold criteria for DSM-V for MDD and/or PTSD. .
- (3) Ability to attend weekly IPT sessions/fluoxetine monitoring in person or by telephone;
- (4) 18 years or older.

Exclusion criteria:

- (1) Cognitive dysfunction compromising ability to participate in IPT or accurately take fluoxetine (lack of orientation to person, place, time and situation);

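### The untreated comparator for the cost-benefit analysis is modelled from depression alone, yet PTSD-only participants are eligible and Hypothesis 4a covers them, so the net gain can be biased in either direction

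*Protocol*

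**What the plan says.** The protocol section Estimation of non-intervention control explains that, for ethical reasons, there is no untreated arm. It then describes a modelled one in four steps, each framed in terms of depression:

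- **Care represented:** "we will compare the interventions to current (mainly absent) depression management".
- **Why a before-after comparison is refused:** "the natural history of untreated depression involves (at least episodic) clinical resolution in a substantial subset of individuals".
- **Source of the untreated course:** the association of clinical and economic status seen under treatment is applied "to historical data on the natural history of depression in these settings".
- **Productivity link:** the assumption is that "changes in productivity associated with clinical resolution of the depression episode following treatment can be applied to untreated patients who eventually remit".

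The population and the claim are wider. Inclusion criterion (1) admits "adult primary care outpatient clinic attendees who meet the threshold criteria for DSM-V for MDD and/or PTSD". Aim 4 concerns both disorders, and Hypothesis 4a reads: "Pooled cost-benefit ratios will show that depression and/or PTSD treatment leads to net economic gain for individuals and households at month 6". Measurement of implementation costs counts screening and treatment for MDD and/or PTSD. Cost-benefit analyses plans results for the two treatments together and separately, but not by diagnosis. The SAP has no cost-benefit section. It does record that not every participant had both disorders at baseline.

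**The concern.** Without a concurrent untreated arm, the benefit credited to treatment is the outcome under treatment minus the modelled untreated outcome. An error in the modelled course therefore passes directly into the benefit. A participant with PTSD and no MDD has no depression episode to resolve, so neither the remission source nor the productivity link describes that person. Nothing in either document names a PTSD course or removes such participants from Aim 4.

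The protocol accepts that natural recovery is not confined to depression. Under Potential Risks it treats spontaneous remission as a common event among candidates who met the threshold for MDD and/or PTSD and later do not.

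At stake is the net-gain statement of Hypothesis 4a at month 6, and Hypothesis 4b at month 30 wherever it relies on the same comparator. The protocol's Significance section promises policy makers a set of cost-benefit options based on these results. The primary clinical outcomes are not affected.

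**Working it through.** The plan states no figure for the untreated comparator: no untreated remission rate for either disorder, no PTSD-only share and no expected return. There is nothing to reproduce, so the check is a sensitivity calculation.

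**Inputs**

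- Treated remission t = 50%. Sample size calculations assumes that half of participants will need second-line treatment. Applied here to both diagnoses.
- Untreated MDD remission rM = 30%: assumed.
- Untreated PTSD remission rP = 10% to 40%: assumed.
- PTSD-only share w: assumed at 5%, 10% and 26.2%. The last is 710/2710 = 0.262. It would apply if the 2000 participants whom the abstract describes as having MDD all do, and the 710 added as MDD and/or PTSD all have PTSD only. It is not a firm ceiling, because the current inclusion criterion applies and/or to everyone.

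**Formulas**

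- Increment as planned (depression course for all): t − rM
- Increment with a diagnosis-specific course: t − [(1 − w)·rM + w·rP]
- Planned minus diagnosis-specific: w·(rP − rM)

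The difference is zero only if rP = rM (or w = 0), and its sign follows rP − rM.

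**Results.** The planned increment is 50 − 30 = 20.0 points in every row.

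| w | rP | Untreated, mixed | Increment, mixed | Planned / mixed |
|---|---|---|---|---|
| 5% | 10% | 28.5 + 0.5 = 29.0 | 21.0 | 0.952 |
| 5% | 40% | 28.5 + 2.0 = 30.5 | 19.5 | 1.026 |
| 10% | 10% | 27.0 + 1.0 = 28.0 | 22.0 | 0.909 |
| 10% | 40% | 27.0 + 4.0 = 31.0 | 19.0 | 1.053 |
| 26.2% | 10% | 22.1 + 2.6 = 24.8 | 25.2 | 0.792 |
| 26.2% | 40% | 22.1 + 10.5 = 32.6 | 17.4 | 1.151 |

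At rP = 30% every row would give 20.0 and a ratio of 1. So the planned increment is about 5% too low to 3% too high at a 5% share, and about 21% too low to 15% too high at 26.2%.

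The percentages also depend on rM. At w = 26.2% and the same PTSD range, rM = 20% gives ratios of 0.92 to 1.21, and rM = 40% gives 0.56 to 1.00.

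In absolute terms, if the two untreated rates differ by 30 points either way, untreated remission is wrong by 1.5 points at w = 5%, 3.0 at 10% and 7.9 at 26.2%.

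**The case against.** The best defence is that this is an unspecified input rather than a wrong one. If untreated MDD and PTSD remit at similar rates, the planned method has no error on this account, and the documents do not show that they differ. The preliminary Kisumu data give 38% MDD and 52% PTSD remission with IPT, but those are treated rates. The abstract also suggests that most participants have MDD and that comorbidity is common, so the PTSD-only share may be small. All of this stands, and it limits the size of the point. It does not supply a reason to assume equal rates.

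A second defence is that benefit is more than remission. The plan also uses health care utilization, hospitalization and mortality, and it calls conservative the step of crediting untreated remitters with treated productivity gains. It is fair that a remission difference is a simplification. But the conservative step sets the value of each untreated remission; it does not say how many PTSD-only participants would remit.

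A reader might go further and infer that PTSD-only participants get no counterfactual at all, so that all their recovery is credited to treatment and the net gain is overstated. The documents do not support that. It would amount to comparing these patients with their own baseline, which the section rules out in general terms. The more natural reading is that the depression course is applied to everyone, and then the error can have either sign.

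Nor does the word pooled in Hypothesis 4a mean pooling over diagnoses: Cost-benefit analyses uses it for IPT and fluoxetine taken together. PTSD-only participants enter because the hypothesis is worded for depression and/or PTSD and no diagnosis split is planned.

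**Conclusion.** The point holds as a mismatch between the modelled comparator and the population to which the claim refers. As written, PTSD-only participants are given a depression course that the documents do not justify for them, and the net-gain estimate is biased unless the two untreated rates coincide. Neither direction nor size can be determined from the documents. The illustrative range of about −5% to +3% at a 5% share and −21% to +15% at a 26.2% share rests on assumed shares, assumed untreated rates, a 50% treated remission common to both diagnoses, and benefit proportional to incremental remission. It is a modest point about the economic aim, and it is cheap to correct.

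**What to change.** Revise Estimation of non-intervention control so that the untreated course is built by baseline diagnosis and weighted to the enrolled mix. For PTSD-only participants, name a PTSD natural-course source, set low, middle and high values, and show the cost-benefit ratio at each. State also which productivity change is attached to PTSD resolution, since the present link refers only to a depression episode. Use the same comparator wherever Hypothesis 4b depends on it. Baseline diagnosis is already collected, so no new participant data are needed. The cost is a search for the PTSD input, a short protocol revision, one sensitivity table and a wider reported range.

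The alternative is to restrict the ratios and the claim to participants with MDD at baseline. This avoids the PTSD-only input, but it narrows Aim 4 and shrinks the analysis set. The implementation costs, now measured jointly for MDD and/or PTSD, would have to be restricted to match.

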Cost-benefit analyses. An important question for policymakers concerns the economic returns to investments in treating and improving mental health. We will use data obtained on the economic status of those treated to calculate the economic benefits associated with treated mental health disorders (both pooled analyses of IPT or fluoxetine treatment and separate analyses of IPT and fluoxetine treatment). We will also incorporate data on health care utilization and hospitalizations (Table 1). The value of these economic benefits will be summarized on a per-person basis and then combined with the implementation cost data to generate a rate of return on mental health expenditures (in general and by treatment type –IPT or fluoxetine). This rate of return is net gains in all economic measures divided by implementation costs, x 100 to yield % return. Cost and income measures will be adjusted for inflation and discounting during the 3 year study period.

Human participants in the project

Target population. Adult primary care outpatient clinic attendees at Kisumu County Hospital (KCH) and other Kisumu County Ministry of Health facilities.

Sample size calculations: SMART designs are used to inform the construction of optimal Adaptive Treatment Strategies (ATS), which is our goal. Therefore, we will power our study to detect the smallest difference between the various ATS included in the study design. The proposed SMART examines (1) first line treatment strategies with IPT or fluoxetine, including long-term relapse risk for participants who remit with initial treatment and (2) second line treatment strategies for non-remitters—specifically, treatment “switch” (from IPT to fluoxetine or vice versa) versus treatment “combination” (addition of IPT to fluoxetine or vice versa). Based on the current evidence base, we

expect that differences between switching or combining treatment will be smaller than other ATS comparisons in the study and we will therefore power the study to detect this difference.

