As it pertains to antidepressants and psychotherapy, the evidence base comparing “switching” versus “combining” treatment for non-remitters (second line treatment) is still developing. However, the field does have meta-analytic data on the differences between treating depression with antidepressants or psychotherapy alone, versus their combination. A 2009 meta-analysis (n=2036) which compared combination treatment (psychotherapy and pharmacotherapy) to pharmacotherapy alone for depression found an effect size of 0.31 (Cohen’s d).²⁷ A 2007 meta-analysis (n=903) found that the remission rate for major depression treated with psychotherapy and pharmacotherapy was better than psychotherapy alone, with an odds ratio of 1.5928, which when converted to a Cohen’s d is 0.25.²⁹ While specific studies have not yet been completed for IPT and PTSD, we leveraged the above-referenced meta-analyses of the effects of general psychotherapy and general pharmacotherapy to estimate sample size for the proposed study. Based on those studies, we would need approximately 164 per treatment arm to compare combined psychotherapy-medication treatment with medication alone, and 242 to compare combined psychotherapy-medication with psychotherapy, alone (using a two-sided alpha of 0.05 and power of 0.80). Using the conservative estimate, we will need 242 for each of the four treatment arms (968, total) after the second randomization (switch to fluoxetine, switch to IPT, combination after fluoxetine, combination after IPT). Note, this strategy uses fluoxetine treatment for 6 months as a first line treatment,

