Project Title: SMART-DAPPER: Leveraging the Depression And Primary-care Partnership for Effectiveness-implementation Research Project (SMART-DAPPER)

Clinicaltrials.gov number: NCT03466346

Title of Document: Statistical Analysis Plan

Date of Document: October 27, 2021

Statistical Analysis Plan

We used an intent-to-treat analysis. We used multivariate normal multiple imputation with 100 imputations to impute missing values of BDI-2 and PCL-5. For both of our primary outcomes (binary) we used generalized estimating equations (GEE) methods to fit a log-link binomial regression model with robust standard errors and a working exchangeable correlation structure to accommodate the repeated measures over time. Because not all participants had both major depression and PTSD at baseline, our analysis models the change in the risk of the outcome from baseline to end of first-line treatment.

Correspondingly, our model included the predictors of time (e.g., baseline and end of treatment), intervention group, the interaction of time, and intervention group. Results are described in terms of relative risks, and, for the interaction, ratios of relative risks with corresponding confidence intervals. The primary test of interest is the time by group interaction.

Secondary outcomes (BDI-2, PCL-5 continuous scores) were numeric, continuous variables. For these analyses we used GEE methods to fit a linear regression model with robust standard errors and a working exchangeable correlation structure. As before, our model included the predictors of time (baseline, end of treatment), intervention group and the interaction of time and intervention group. Results are described in terms of differences in mean values and, for the interaction, differences of differences with corresponding confidence intervals. The primary test of interest is the time by group interaction.

Participants who were not in remission at end of first line treatment were re-randomized to either treatment switch or treatment combination. These randomized comparisons were conducted using Fisher's exact test for MDD or PTSD or an exact Wilcoxon rank-sum test for BDI-2 score or PCL-5 score.

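### The SAP tests first-line arms and second-line arms separately but specifies no comparison of the four embedded strategies, although finding the optimal strategy is the stated goal

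*Protocol*

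**What the plan says.** The Protocol's section on sample size calculations sets the aim: "SMART designs are used to inform the construction of optimal Adaptive Treatment Strategies (ATS), which is our goal". It then gives the powering basis: "we will power our study to detect the smallest difference between the various ATS included in the study design". The authors "expect that differences between switching or combining treatment will be smaller than other ATS comparisons in the study", so the calculation is done for switch versus combination: "we will need 242 for each of the four treatment arms (968, total) after the second randomization".

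The SAP has two sets of analyses:

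- **First line.** An intention-to-treat GEE covers baseline and end of first-line treatment. The time-by-group interaction is the main test for the two binary outcomes, and BDI-2 and PCL-5 scores are handled in the same way.
- **Second line.** "Participants who were not in remission at end of first line treatment were re-randomized to either treatment switch or treatment combination". These arms are compared by Fisher's exact test or an exact Wilcoxon rank-sum test.

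The Protocol adds three relevant hypotheses. Hypothesis 1a concerns remission by initial treatment. Hypothesis 1b concerns relapse among remitters, analysed by weighted GEE through month 30. Hypothesis 3c says Q learning will yield personalised algorithms. The SAP takes up neither relapse nor Q learning, and the Protocol's data analysis plan has no Q-learning text.

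**The concern.** A strategy is a whole path: a first treatment, what follows remission, and what follows non-remission. Its value is the outcome averaged over everyone who starts on it. The SAP's first analysis stops before second-line treatment begins. Its second leaves out everyone who remitted on first-line treatment, a share the Protocol takes to be half. No specified analysis joins the two.

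The Protocol's own hypotheses make this matter. Hypothesis 1a expects similar remission whichever treatment comes first, while Hypothesis 1b expects fewer relapses after IPT or combination. If both are right, the difference between starting treatments appears mainly after the point where the SAP's first-line analysis ends. The trial could then follow its SAP exactly and still not say which of the four strategies gives the best result at a common time, or with what uncertainty.

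**Working it through.** **1. The plan's own sample size.** The inputs are from the Protocol: "using a two-sided alpha of 0.05 and power of 0.80"; for combination versus medication, a meta-analysis that "found an effect size of 0.31"; for combination versus psychotherapy, a result "with an odds ratio of 1.5928, which when converted to a Cohen’s d is 0.25". I read the odds ratio as 1.59 followed by a run-on citation number, 28.

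Per arm, n = 2(1.960 + 0.842)²/d² = 15.70/d², rounded up.

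- d = 0.31: 15.70/0.0961 = 163.4, so 164 (stated 164).
- OR 1.59: d = ln(1.59) × √3/π = 0.2557; 15.70/0.0654 = 240.1, so 241 (stated 242; d = 0.255 gives 242). The printed d = 0.25 would give 252.
- 242 × 4 = 968, and 968/0.5 = 1936.

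The figure reproduces. It is a calculation for pairs of second-line arms among non-remitters. No contrast between strategies with different first treatments is sized.

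**2. Which contrasts are covered.** Four strategies give 4 × 3/2 = 6 pairs. Two pairs share a first treatment, and a second-line test within that first-line arm informs them. The SAP does not say whether its second-line tests are run within each first-line arm or pooled, so even these two need confirming. The other four pairs cross first treatments.

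| Analysis | Who is included | Why it gives no strategy value |
|---|---|---|
| SAP GEE; Hypothesis 1a | All randomised | Ends at or before the end of first-line treatment |
| SAP Fisher and Wilcoxon tests | Non-remitters | Excludes first-line remitters |
| Hypothesis 1b | Remitters | Excludes those who do not remit |
| Hypothesis 3c | Not stated | No method in either document |

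**3. What a strategy comparison could show.** The documents give no second-line remission rates, so this is illustrative. Let r be first-line remission (0.50 in the Protocol), q the share of remitters still well at the endpoint (assumed 0.6 to 1.0), and p the second-line remission rate (assumed 0.3 to 0.5). With n participants per first-line arm:

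- Value = r·q + (1 − r)·p
- Variance = [r·q(1 − q) + 2(1 − r)·p(1 − p) + r(1 − r)(q − p)²]/n

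Take n = 1936/2 = 968, r = 0.5, q = 1, p = 0.3. The bracket is 0 + 0.2100 + 0.1225 = 0.3325. The standard error of a different-start contrast is √(2 × 0.3325/968) = 0.0262. The difference detectable with 80% power is 2.802 × 0.0262 = 7.3 points. Over the assumed ranges of q and p it is 7.1 to 7.8 points.

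A second-line odds ratio of 1.59 moves p from 0.30 to 0.405, or from 0.50 to 0.614. That is 10.5 to 11.4 points among non-remitters. Multiplied by 1 − r = 0.5, it is 5.3 to 5.7 points at strategy level.

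Power for that difference between strategies with different starts:

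- r = 0.50: 49% to 64%; 80% power needs about 2840 to 4100 analysable participants.
- r = 0.33: 69% to 79%.
- r = 0.67: 27% to 45%.
- r = 0.50, with 40% of 2710 lost (1626 left, 813 per first-line arm): 42% to 56%.

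The Protocol mentions first-line remission of about one third and over two thirds, so all three values of r are plausible.

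**The case against.** The strongest reply is that the SAP tests the comparison that was sized. Directly after the goal sentence, the Protocol lists what the SMART examines: first-line treatments, including relapse, and second-line switch versus combination. The goal is to inform the construction of strategies, which stage-wise randomised comparisons do, and no hypothesis under Aims 1 to 6 ranks four strategies. This stands in part. A reader might infer that the trial was sized to rank the strategies. It was not: a strategy difference is the stated basis, but the calculation is for second-line arms.

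A reader might also infer that the SAP tests only second-line arms, or that different starting treatments are never compared. Both are wrong. The SAP's primary analysis compares first-line IPT with fluoxetine in all randomised participants, and Hypothesis 1b compares relapse across treatments.

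It can also be said that the pieces could be combined afterwards as r + (1 − r)·p. That is true if remission counts once achieved, but the result depends on a definition nobody has fixed. With r = 0.5 and p = 0.3, it gives 0.5 + 0.15 = 0.65. If only 60% of remitters are still well at the endpoint, it is 0.30 + 0.15 = 0.45. What is missing is a pre-specified outcome, time point, estimator and interval, not the data.

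Lastly, limited power argues against formal tests among the four strategies. It does not argue against estimates with intervals.

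**Conclusion.** The point holds as an omission. Optimal strategies are the stated goal and the smallest strategy difference is the stated powering basis. Yet the SAP specifies no comparison of the four embedded strategies and no Q-learning method. No planned analysis gives a strategy-level remission rate that includes both remitters and non-remitters. Four of six pairwise contrasts have no specified estimator, and the other two are covered only if the second-line tests are run within first-line arms.

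The first-line primary test and the randomised second-line tests remain valid, so this is a change that should be made rather than a fatal flaw. The count follows from the design alone. The power figures rest on assumed values of q and p and on equal allocation at both randomisations.

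**What to change.** Add a secondary, estimation-focused analysis of the four strategies:

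- **Outcome.** Remission at one common visit. Month 12 appears on every path in the Figure 3 footnotes and in the Protocol's assessment schedule.
- **Estimator.** Weighted-and-replicated GEE with robust variance clustered on participant. Each first-line remitter is replicated to both strategies consistent with their path.
- **Weights.** The inverse of the actual randomisation probabilities. If both randomisations are 1:1, these are 1/0.5 = 2 for remitters and 1/(0.5 × 0.5) = 4 for non-remitters. The equal 242 per arm implies 1:1 re-randomisation, but the text does not state it, so the SAP should.
- **Covariates.** Baseline BDI-2 and PCL-5, sex and delivery mode.
- **Dropout before re-randomisation.** Extend the planned multiple imputation to remission status, or use censoring weights.
- **Reporting.** Four strategy-specific remission rates and their contrasts with confidence intervals, and a statement that precision for different-start contrasts is limited.

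Say whether the second-line tests are run within first-line arms. Give Hypothesis 3c a method, or state that it is handled in a separate plan. Label the new analysis as added after the SAP of October 27, 2021.

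The alternative is to restate the goal in the sample size section as stage-wise comparisons.

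The cost is one further analysis of data already scheduled for collection, plus the work on dropout. Trial conduct does not change.
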